**LIST OF ABBREVIATIONS**

AE	Adverse Event
AESI	Adverse Events of Specific Interest
BMI	Body Mass Index
CI	Confidence Interval
eCRF	electronic Case Report Form
ES	Exposed Set
IDMC	Independent Data Monitoring Committee
ILI	Influenza-Like Illness
LL	Lower Limit of the confidence interval
MAE	Medically Attended Event
MedDRA	Medical Dictionary for Regulatory Activities
N.A.	Not Applicable
pIMD	Potential Immune-Mediated Disease
SAE	Serious Adverse Event
SAP	Statistical Analysis Plan
SBIR	GSK Biological's Internet Randomization System
SD	Standard Deviation
SRT	Safety Review Team
SUSAR	Suspected Unexpected Serious Adverse Reactions
TFL	Tables Figures and Listings
TOC	Table of Content
UL	Upper Limit of the confidence interval

## 1. DOCUMENT HISTORY

Date	Description	Protocol Version
26 JAN 2018	First version	Amendment 1 – 24 October 2017
18 JUL 2018	Amendment 1: The following changes were made: - Alignment with Protocol Amendment 2 (in bold italic) - Corrections (in bold italic) - Update of templates	Amendment 2 – 16 March 2018
11 FEB 2019	Amendment 2: The following changes were made: - Alignment with Protocol Amendment 3 (in bold italic) - Corrections (in bold italic) - Update of templates	Amendment 3 - 07 December 2018
12 SEP 2019	Amendment 3: The following changes were made: - Alignment with Protocol Amendment 4 (in bold italic and by deleting) - Addition of Section 10 (new SAP template) - Change in Sections 11 and 12.2.5 (in bold italic)	Amendment 4 - 11 July 2019

## 2. STUDY DESIGN

\*If a subject presents signs and symptoms of influenza-like illness (ILI), nasal and throat swabs will be collected as soon as possible (preferably within 24 hours, but not later than 7 days) after the onset of an ILI to test for influenza and/or other respiratory pathogens by RT-PCR **if deemed necessary or for storage**.

\*\*IDMC reviews will be performed throughout the study.

- **Experimental design:** Phase I/II, observer-blind, randomized, controlled, multi-centric study with 10 parallel groups.
- **Study groups:**
  - **cH8/P/cH5-AS03 group:** 47 subjects receiving one dose of cH8/1N1+AS03 at Day 1, one dose of PBS at Day 57 and one booster dose of cH5/1N1+AS03 at Month 14.
  - **cH5/P/cH8-AS03 group:** 47 subjects receiving one dose of cH5/1N1+AS03 at Day 1, one dose of PBS at Day 57 and one booster dose of cH8/1N1+AS03 at Month 14.
  - **cH8/5/11-AS03 group:** 47 subjects receiving one dose of cH8/1N1+AS03 at Day 1, one dose cH5/1N1+AS03 at Day 57 and one booster dose of cH11/1N1+AS03 at Month 14.
  - **cH8/P/cH5-AS01 group:** 47 subjects receiving one dose of cH8/1N1+AS01 at Day 1, one dose of PBS at Day 57 and one booster dose of cH5/1N1+AS01 at Month 14.
  - **cH5/P/cH8-AS01 group:** 47 subjects receiving one dose of cH5/1N1+AS01 at Day 1, one dose of PBS at Day 57 and one booster dose of cH8/1N1+AS01 at Month 14.
  - **cH8/5/11-AS01 group:** 47 subjects receiving one dose of cH8/1N1+AS01 at Day 1, one dose cH5/1N1+AS01 at Day 57 and one booster dose of cH11/1N1+AS01 at Month 14.
  - **cH8/P/cH5 group:** 47 subjects receiving one dose of cH8/1N1 at Day 1, one dose of PBS at Day 57 and one booster dose of cH5/1N1 at Month 14.
  - **cH5/P/cH8 group:** 47 subjects receiving one dose of cH5/1N1 at Day 1, one dose of PBS at Day 57 and one booster dose of cH8/1N1 at Month 14.
  - **cH8/5/11 group:** 47 subjects receiving one dose of cH8/1N1 at Day 1, one dose cH5/1N1 at Day 57 and one booster dose of cH11/1N1 at Month 14.
  - **IIV4 group:** 47 subjects receiving one dose of *Fluarix Quadrivalent* at Day 1, one dose of PBS at Day 57 and one dose of *Fluarix Quadrivalent* at Month 14.
- **Treatment allocation:** randomized (1:1:1:1:1:1:1:1:1 ratio) using GSK Biologicals' Randomization System on Internet (SBIR). The randomization algorithm will use a minimization procedure accounting for center, sex, age (18-30 years vs. 31-39 years) and history of influenza vaccination since the 2014/2015 season (yes vs. no).

- **Enrolment:** the study will follow a staggered enrolment with 2 steps; the first being Phase I (N = ~80) and the second being Phase II (N = ~390):
  - Phase I: During the Phase I enrolment, subjects will be vaccinated one at a time, at least 60 minutes apart, with a maximum of 10 subjects/day until ~80 subjects are enrolled (i.e. to obtain treatment groups of at least 8 subjects/group). If no safety issue is identified by the Independent Data Monitoring Committee (IDMC) upon review of the 7-day post-dose 1 safety data (Days 1-7) of all Phase I subjects (N = ~80), Phase II enrolment will be allowed to start.
  - Phase II: Subjects will be enrolled and vaccinated without limitation on the number of vaccinees per day or time between consecutive subjects.
- **Vaccination schedule:**
  - Two primary doses at Visit 1 (Day 1) and Visit 4 (Day 57).
  - A booster dose at Visit 8 (Month 14).
- **Definition of the different epochs:**
  - Epoch 001: Screening (Day -28 to -2) – only for Phase I subjects.
  - Epoch 002: Primary starting at Visit 1 (Day 1) and ending at Visit 7 (Month 8).
  - Epoch 003: Booster starting at Visit 8 (Month 14) and ending at Visit 12 (Month 26).

- **Intervals between study visits**

Interval	Optimal length of interval	Allowed interval**
Screening to Visit 1*	2-28 days	
Visit 1 → Visit 2	7 days	7-9 days
Visit 1 → Visit 3	28 days	28-38 days
Visit 1 → Visit 4	56 days	56-66 days
Visit 4 → Visit 5	7 days	7-9 days
Visit 4 → Visit 6	28 days	28-38 days
Visit 4 → Visit 7	168 days	168-196 days
Visit 4 → Visit 8	336 days	336-364 days
Visit 8 → Visit 9	7 days	7-9 days
Visit 8 → Visit 10	28 days	28-38 days
Visit 8 → Visit 11	168 days	168-196 days
Visit 8 → Visit 12	336 days	336-364 days

\* Only applicable for Phase I subjects. Screening evaluations may be completed 2 to 28 days before Day 1. Site staff should allow sufficient time between the screening and Day 1 visits to receive and review screening safety laboratory test results. If a delay occurs such that the interval between screening and the Day 1 vaccination exceeds 28 days, a re-screening visit should be scheduled before Visit 1.

\*\* Visits out of the allowed interval can lead to elimination from the Per-Protocol set for immunogenicity analysis.

- **Sampling schedule:**

- Blood samples for safety assessment will be drawn from all subjects at all visits: Screening\*, Days 1, 8, 29, 57, 64, 85, Month 8, Month 14, Month 14 + 7 days, Month 14 + 28 days, Month 20 and Month 26.

\*Only for subjects enrolled in Phase I (refer to the protocol).

**Table 1** Hematology/biochemistry

System	Discipline	Component	Method	Scale**	Laboratory
Whole blood	Hematology	Leukocytes (white blood cells)	As per central laboratory procedure	Quantitative	Central laboratory***
		Neutrophils*			
		Lymphocytes*			
		Basophils*			
		Monocytes*			
		Eosinophils*			
		Hemoglobin			
		Platelets			
		Erythrocytes (red blood cells)			
Serum	Biochemistry	Alanine aminotransferase (ALT)	As per central laboratory procedure	Quantitative	
		Aspartate aminotransferase (AST)			
		Creatinine 			
		Urea nitrogen 			

\*For white blood cell differential count.

\*\*Grading of laboratory parameters will be based on the Food and Drug Administration (FDA) Guidance for Industry "Toxicity Grading Scale for Healthy Adult and Adolescent Volunteers Enrolled in Preventive Vaccine Clinical Trials" (refer to the Appendix C of the protocol).

\*\*\*Refer to the Appendix B of the protocol for the laboratory addresses

1 The Blood Urea Nitrogen (BUN)-to-creatinine ratio is to be calculated.

- Blood samples for serology testing will be drawn from all subjects at Days 1 (Visit 1), 29 (Visit 3), 85 (Visit 6), Month 8 (Visit 7), Month 14 (Visit 8), Month 14 + 28 days (Visit 10), Month 20 (Visit 11) and Month 26 (Visit 12).
- Blood samples for passive transfer experiment in animals will be drawn from all subjects at Days 1 (Visit 1), 85 (Visit 6), Month 14 (Visit 8)\*.
- Blood samples for cell-mediated immunity (CMI) assessment will be drawn from a sub-cohort of ~225 subjects at Days 1 (Visit 1), 8 (Visit 2), 29 (Visit 3), 64 (Visit 5), 85 (Visit 6), Month 14 (Visit 8)\*, Month 14 + 7 days (Visit 9)\* **and** Month 14 + 28 days (Visit 10)\*. The sub-cohort will consist of the first Phase II subjects enrolled in pre-specified centers.

*\*Note that samples already collected for these timepoints by the time of Protocol Amendment 4 implementation at site will not be tested and will be stored, unless deemed necessary based on medical review of the cases.*

**Table 2 Immunological read-outs for humoral immunity and cell-mediated immunity**

Blood sampling timepoint		Sub-cohort Name	No. subjects	Component	Components priority rank		
Type of contact and timepoint	Sampling timepoint						
Humoral immunity							
Visit 1 (Day 1)	PRE	All subjects	~470	Anti-H1 HA stalk ELISA	P P		
Visit 3 (Day 29)	Pld28			Anti-H2 HA full length ELISA	P P		
Visit 6 (Day 85)	PIld28			Anti-H18 HA full length ELISA	P P		
Visit 7 (Month 8)	M8			Anti-H1 HA stalk MN assay	P P		
Visit 8 (Month 14)	M14			Anti-heterosubtypic HA Group 1 virus MN assay (H1N1 swine)	P P		
Visit 10 (Month 14 + 28 days)	PIIld28			Anti-heterosubtypic HA Group 1 virus MN assay (IIV4 H1N1 strains)	P P		
Visit 11 (Month 20)	M20	All subjects	~470	HI with cH5/1N1 and cH8/1N1 virus	P P		
Visit 12 (Month 26)	M26						
Cell-mediated immunity							
Visit 1 (Day 1)	PRE			T-cell response by ICS assay	P P		
Visit 3 (Day 29)	Pld28	CMI sub-cohort*	~225	B memory cells by ELISPOT	P		
Visit 6 (Day 85)	PIld28				P		
Visit 1 (Day 1)	PRE			Plasmablast detection to HA by flow cytometry	P		
Visit 2 (Day 8)	Pld7				P		
Visit 3 (Day 29)	Pld28				P		
Visit 5 (Day 64)	PIld7				P		
Visit 6 (Day 85)	PIld28						

PRE = pre-vaccination; PI = post-dose 1; PII = post-dose 2; PIII = post-dose 3 (booster); D = day; M = month; ELISA = enzyme-linked immunosorbent assay; MN = microneutralization; IIV4 = quadrivalent inactivated influenza vaccine; ICS = intracellular cytokine staining

\*CMI sub-cohort comprising ~225 Phase II subjects.

In case of insufficient blood sample volume to perform assays for all antibodies, the samples will be analyzed according to priority ranking provided in [Table 2](#).

- **Influenza-like illness (ILI) surveillance:** ILI is defined as at least one of these systemic symptoms:

- Temperature (oral)  $\geq 37.8^{\circ}\text{C}/98.6^{\circ}\text{F}$  and/or,
- Myalgia (widespread muscle ache);

AND at least one of these respiratory symptoms:

- Cough and/or,
- Sore throat.

Passive surveillance will be carried out from Visit 1 (after Dose 1) until the end of the study (Visit 12). Subjects will be instructed to contact the investigator/study staff as soon as they experience ILI symptoms. During the entire study period, nasal and throat swabs will be collected as soon as possible (preferably within 24 hours, but not later than 7 days) after the onset of an ILI to test for influenza and/or other respiratory pathogens by RT-PCR *if deemed necessary, or stored for future research.*

All cases of ILI have also to be recorded as unsolicited adverse event (AE) or serious adverse event (SAE) in the electronic Case Report Form (eCRF).

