#### **6.3.1. Analysis of safety planned in the protocol**

- The percentage of subjects with at least one local AE (solicited and unsolicited), with at least one general AE (solicited and unsolicited) and with any AE during the solicited follow-up period will be tabulated with exact 95% CI. The same calculations will be performed for AEs rated as grade 3.
- The percentage of subjects reporting each individual solicited local and general AE during the solicited follow-up period will be tabulated with exact 95% CI. The same tabulation will be performed for grade 3 AEs and for AEs with causal relationship to vaccination.

- The verbatim reports of unsolicited AEs will be reviewed by a physician and the signs and AEs will be coded according to the Medical Dictionary for Regulatory Activities (MedDRA). The percentage of subjects with at least one report of unsolicited AE classified by the MedDRA and reported up to 28 days after vaccination will be tabulated with exact 95% CI. The same tabulation will be performed for grade 3 unsolicited AEs and for unsolicited AEs with causal relationship to vaccination.
- The percentage of subjects with Medically Attended Event(s) (MAE(s)) will be summarized by group with exact 95% CI.
- The percentage of subjects with episode(s) of ILI will be summarized by group with exact 95% CI.
- At each hematology/biochemistry sampling timepoint, by study group, individual hematological and biochemical values will be presented as number of subjects out of range (above and below normal range) and tabulated by toxicity grading (refer to Appendix C of the protocol). In addition, changes from baseline (median/interquartile range) will be presented.
- SAEs and pIMDs will be described in detail. Withdrawals due to (S)AEs will also be summarized.

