### 12.2.3. Demography

Baseline measurements will be defined as the one closest to first vaccination date or on the date of first vaccination (but not later).

The age will be computed as the number of units between the date of birth and the reference activity. Note that as the day is not collected, the derived age may be incorrect by up to 1 month. This may lead to apparent inconsistency between the derived age and the eligibility criteria/the age category used for randomization.

Unit conversions for weight, height and temperature are done at the level of the SDTM data using the below rules:

- Conversion of weight to kg:
  - Weight in Kilogram = weight in Pounds \* 0.45359237
- Conversion of height to cm:
  - Height in Centimeters = Height in Inch \* 2.54.
- Conversion of temperature from °Fahrenheit to °Celsius
  - Temperature in °Celsius = ((Temperature in °Fahrenheit -32) \*5)/9

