**Table 5 Intensity scales for solicited symptoms**

Adverse Event	Intensity grade	Parameter
Pain at injection site	0	None
	1	Mild: Any pain neither interfering with nor preventing normal everyday activities.
	2	Moderate: Painful when limb is moved and interferes with everyday activities.
	3	Severe: Significant pain at rest. Prevents normal everyday activities.
Redness at injection site		Record greatest surface diameter in mm
Swelling at injection site		Record greatest surface diameter in mm
Fever*		Record temperature in °C/F
Headache	0	Normal
	1	Mild: Headache that is easily tolerated
	2	Moderate: Headache that interferes with normal activity
	3	Severe: Headache that prevents normal activity
Fatigue	0	Normal
	1	Mild: Fatigue that is easily tolerated
	2	Moderate: Fatigue that interferes with normal activity
	3	Severe: Fatigue that prevents normal activity
Gastrointestinal symptoms (nausea, vomiting, diarrhea and/or abdominal pain)	0	Normal
	1	Mild: Gastrointestinal symptoms that are easily tolerated
	2	Moderate: Gastrointestinal symptoms that interfere with normal activity
	3	Severe: Gastrointestinal symptoms that prevent normal activity
Arthralgia	0	Normal
	1	Easily tolerated
	2	Interferes with normal activity
	3	That prevents normal activity
Myalgia	0	Normal
	1	Easily tolerated
	2	Interferes with normal activity
	3	That prevents normal activity
Shivering	0	Normal
	1	Easily tolerated
	2	Interferes with normal activity
	3	That prevents normal activity

\*Fever is defined as temperature  $\geq 38.0^{\circ}\text{C} / 100.4^{\circ}\text{F}$ . The preferred location for measuring temperature in this study will be the oral cavity.

The maximum intensity of local injection site redness/swelling/fever will be graded at GSK Biologicals as follows:

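### The ILI definition gives one oral temperature threshold as 37.8°C/98.6°F, but the two figures are different temperatures (0.8°C apart), so ILI status in that band depends on the scale used

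*SAP*

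**What the plan says.** Section 2 (Study design, ILI surveillance) requires one systemic and one respiratory symptom. The systemic part is met by an oral temperature at or above "37.8^{\circ}\text{C}/98.6^{\circ}\text{F}$ and/or", or by "Myalgia (widespread muscle ache"). The respiratory part is joined by "AND at least one of these respiratory symptoms", namely cough or sore throat. The same pair of temperatures stands in the first SAP version and in Amendments 1, 2 and 3.

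Section 12.2.3 gives the conversion rule for the analysis data: "Temperature in °Celsius = ((Temperature in °Fahrenheit -32) \*5)/9". For the solicited symptom fever, Table 5 says "Record temperature in °C/F", and its footnote sets fever at 38.0°C/100.4°F.

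The ILI definition feeds these outputs:
- Section 6.3.1: "The percentage of subjects with episode(s) of ILI will be summarized by group with exact 95% CI".
- Section 6.3.2: the percentage with grade 3 ILI, any and RT-PCR-confirmed.
- Template 23: ILI episodes tabulated by the observed combination of temperature, myalgia, cough and sore throat.

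Section 2 also requires every ILI case to be recorded as an unsolicited AE or an SAE.

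**The concern.** A threshold written in two units should be one temperature. Here it is not, and the gap is too large to be rounding. A case definition that classifies the same reading differently in °C and °F leaves the analyst with two cut-offs and no rule for choosing between them. It also lets the recorded ILI status depend on which figure was read.

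At stake are the level and comparability across centers of the ILI percentages, the temperature category in Template 23, and which events are recorded as ILI adverse events. The SAP provides for Fahrenheit readings through its conversion rule and the recording instruction for fever. It does not say that ILI status is re-derived from the converted temperature.

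**Working it through.** **Inputs**
- ILI limit: 37.8°C/98.6°F (Section 2).
- Conversion: C = (F − 32) × 5/9 (Section 12.2.3); inverse F = C × 9/5 + 32.
- Comparison pair: solicited fever, 38.0°C/100.4°F (Table 5 footnote).

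**Step 1. Check the formula on the fever pair.** (100.4 − 32) × 5/9 = 38.0°C. The pair reproduces exactly, so the formula and the document's handling of dual units are sound there.

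**Step 2. Try to reproduce the ILI pair.**
- From the Fahrenheit side: (98.6 − 32) × 5/9 = 37.0°C, not 37.8°C.
- From the Celsius side: 37.8 × 9/5 + 32 = 100.04°F, not 98.6°F.

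The stated pair is not reproduced.

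**Step 3. Size of the gap.** 37.8 − 37.0 = 0.8°C; 100.04 − 98.6 = 1.44°F.

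**Step 4. Who changes status.** The discordant band runs from 98.6°F (37.0°C) to just under 100.04°F (37.8°C). A change of ILI status needs all of the following:
- a temperature in that band;
- cough or sore throat, since without one there is no ILI by either limit;
- no myalgia, since myalgia meets the systemic part at any temperature.

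**Step 5. Edge of the band and rounding.** (100.0 − 32) × 5/9 = 37.78°C. Unrounded, a reading of 100.0°F fails a limit of 37.8°C; rounded to one decimal it is 37.8°C and passes. The first SAP version and Amendment 1 rounded converted temperatures to one decimal (their Section 11.2.3). Amendments 2 and 3 state no rounding. Converting to °C therefore does not by itself settle how a reading of 100.0°F is classified.

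**Step 6. Effect on ILI counts.** This would need the ILI rate, the share of episodes without myalgia, and the share of temperatures read in °F. The SAP gives none of these, so no figure or range is offered.

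**The case against.** The arithmetic is not in dispute; the case on the other side is about consequence.

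- **Few subjects can be affected.** The myalgia route and the respiratory requirement narrow the group to that in Step 4. This stands.
- **Little inference rests on ILI.** In the current SAP, ILI as such is not among the endpoints in Section 4. It is a descriptive safety summary, and the decision rule in Section 7 concerns ELISA GMT ratios. ILI status alone removes nobody from the per-protocol set, because elimination code 2060 requires RT-PCR-confirmed H1N1 infection. This stands. The link through swabs is indirect, and testing is now done only if deemed necessary.
- **Groups should be balanced.** Minimisation includes center, so a scale effect tied to center should fall roughly evenly on the groups. This stands as well.
- **Sites work from the protocol and eCRF, which are not at hand.** Whether any site applied 98.6°F cannot be known from the SAP, and the °C/°F recording line is for solicited fever, not for ILI. This limits what can be said about effect, but not the contradiction within the SAP.

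A reader might infer that ILI incidence is inflated, that the definition is much looser at Fahrenheit sites, or that rates differ by site for this reason. The documents do not support those statements. They show no share of Fahrenheit readings, and inflation would presume that the Celsius figure is the intended one.

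**Conclusion.** The point holds as an internal contradiction in an operative case definition. Under the SAP's own formula, the two halves of the ILI temperature limit differ by 0.8°C (1.44°F). Because the same pair appears in all four SAP versions, while the fever pair converts exactly, it is a wrong figure and not an artefact of reading the PDF.

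The consequence is limited. For subjects with cough or sore throat, no myalgia and a temperature from 98.6°F to just under 100.04°F, ILI status depends on which figure is applied. The descriptive percentages in Sections 6.3.1 and 6.3.2, Template 23 and the ILI-related AE records can shift accordingly, by an amount that cannot be computed from the SAP. That a material between-group bias is unlikely rests on the assumption that use of a scale goes with center, on which allocation is minimised. Nothing here shows which of the two limits was intended.

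**What to change.** 1. Reconcile the two values in Section 2 with each other and with the protocol, so that the °C and °F figures are true equivalents. This review does not choose the limit. If site documents carry the same pair, they need the same correction, since changing the SAP alone does not alter collection.
2. State in the SAP that the ILI temperature criterion is applied on one scale, with a rounding rule, for example the converted °C value to one decimal. Without that rule, 100.0°F remains ambiguous against a limit of 37.8°C.
3. If numeric temperatures were collected for ILI episodes, list the episodes with temperature as the only systemic symptom whose status differs between the two limits. The SAP does not show that such values exist: Template 23 presents temperature only as a symptom category. This step is therefore conditional. It also cannot recover episodes that were never reported, because surveillance is passive and starts with the subject.

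The cost is one corrected figure and one sentence in the SAP, plus a short programmed listing where the data allow it and a notice to sites where it applies.

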**Table 3 Molecular Biology for ILI (PCR tests)**

Component	Kit/ Manufacturer	Method	Unit	Laboratory
Nasal swab samples				
Influenza A virus (Flu A) Influenza B virus (Flu B)	In-house	RT-PCR	Qualitative assay (positive/negative)	
Human Influenza A virus subtype H1 (Flu A-H1) Human Influenza A virus subtype H3 (Flu A-H3)	In-house	RT-PCR	Qualitative assay (positive/negative)	
RSV A virus (RSV A) RSV B virus (RSV B)	In-house	RT-PCR	Qualitative assay (positive/negative)	
Human adenovirus (AdV) Human metapneumovirus (MPV) Human enterovirus (HEV) Human parainfluenza virus 1 (PIV1) Human parainfluenza virus 2 (PIV2) Human parainfluenza virus 3 (PIV3) Human parainfluenza virus 4 (PIV4) Human bocavirus (HBoV) Human rhinovirus (HRV) Human coronavirus 229E (CoV 229E) Human coronavirus NL63 (CoV NL63) Human coronavirus OC43 (CoV OC43)	Allplex Respiratory Panel or equivalent 	Multiplex real- time PCR	Qualitative assay (positive/negative)	GSK Biologicals* or designated laboratory

\*GSK Biologicals laboratory refers to the CLS in Rixensart, Belgium; Wavre, Belgium.

